1.1 Objectives

The primary objective:

To study which of the investigational devices, Variant A and Variant B, that gives a correct activation of the display in relation to the level of saturation of the wound dressing.

The secondary objectives:

To study the consequences in case the dressing has been changed too late. In these cases:

- Have there been occurrence of leakage and how has that affected the wound status and surrounding skin?
- Have there been occurrence of maceration and how has that affected the wound status and surrounding skin?

To study the usability

How often are there use errors, such as incorrect dressing application?

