1.2 Design and endpoints

Patients with exuding leg ulcers were included from two different study sites for the clinical investigation. The clinical investigation is a small, explorative study which aimed to include 6 patients. To complete the study each patient underwent three dressing changes with the investigational device. Both study product versions, Variant A and Variant B, were used on each patient, either in order A-B-A or B-A-B. Amount and type of exudate might change over time, in this way the same variant is used at start and end to detect any changes in results. The aim was to get as many observations from Variant A and Variant B respectively.

Between dressing changes the patients were instructed to monitor the display and note if a blue drop (display activation) appeared. At each dressing change the patient and the caregiver checked the display for activation, weighed the dressing, recorded the wound status and eventual incidents.

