1.3 The clinical investigation hypothesis or pass/fail criteria

The activation of the display in relation to the level of saturation of the wound dressing is determined by weighing the dressing after use which is then checked against the specified intervals in the Table below. The level of saturation is deemed to be in correct interval if the weight of the study product (Absorbest Fuktsensor + DryMax Extra Soft) is in the interval 11-26 g for 10x10 cm, 17-62 g for 10x20 cm and 26-109 g for 20x20 cm.

Table 1. Intervals to determine saturation level of the used dressing. Weight includes dressing dry weight and absorbed liquid

Dressing size	Changed too early	Interval for correct change	Changed too late
	Weight of dressing [g]		
10x10 cm	<11	11-26	>26
10x20 cm	<17	17-62	>62
20x20 cm	<26	26-109	>109

Since the study is small, explorative and observational, no statistics are relevant to calculate. The study does not aim to achieve statistical significance between Variant A and Variant B, but to collect data which should form the basis for a comprehensive assessment of the function of the different variants.

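### The leakage and maceration questions are limited to late changes, a class set by a weight that omits leaked fluid, so a dressing can leave the question because it leaked

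*Protocol*

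**What the plan says.** Protocol section 1.1 (Objectives) introduces a secondary objective with "To study the consequences in case the dressing has been changed too late. In these cases". Two questions follow under that condition: "Have there been occurrence of leakage and how has that affected the wound status and surrounding skin" and "Have there been occurrence of maceration and how has that affected the wound status and surrounding skin". No other objective mentions leakage or maceration.

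Section 1.3 assigns the saturation class by weight alone; it is "determined by weighing the dressing after use which is then checked against the specified intervals in the Table below". The late class begins above 26 g (10x10 cm), 62 g (10x20 cm) or 109 g (20x20 cm). The title of Table 1 adds: "Weight includes dressing dry weight and absorbed liquid".

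Section 1.2 describes what is collected, with no restriction by weight class: "At each dressing change the patient and the caregiver checked the display for activation, weighed the dressing, recorded the wound status and eventual incidents". It aims for 6 patients and states: "To complete the study each patient underwent three dressing changes with the investigational device". Section 1.3 rules out inference: "Since the study is small, explorative and observational, no statistics are relevant to calculate".

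**The concern.** The event being studied can alter the condition for being studied. Leakage removes fluid from the dressing. Less fluid means a lower weight, and the weight decides whether the change counts as late and so whether leakage is asked about. A dressing that overflowed at or near the upper limit may be filed as correctly changed and drop out of the description of leakage.

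The objective also speaks of consequences of late change but looks only at late changes. Without the same description for the other changes, a reader cannot tell whether leakage or maceration is more common after late change or about equally common throughout.

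What is at stake is the completeness and interpretability of one secondary, descriptive objective. A leak or macerated skin at a weight classed as correct would also be useful information on how the limits relate to what happens at the wound, and the objective as worded does not ask for it.

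**Working it through.** The plan states no figure that bears on this point, so there is none to reproduce. The check is logical, with one small illustration.

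**Inputs from the protocol**
- Condition on the two questions: changes made too late (1.1).
- Definition of that term: 1.1 gives none and does not refer to one. Table 1 (1.3) has a column with the same term and is the only definition in the document. The link is therefore an inference from the shared term.
- Upper limits U: 26, 62 and 109 g. A weight equal to U lies in the correct interval.
- Weight W = dry weight + absorbed liquid (title of Table 1).
- Number of changes: 6 patients × 3 = 18 (1.2).

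**Step 1. Where a leaking dressing falls.** Let L > 0 be the fluid that escaped, in grams. The weighed quantity is W; had nothing escaped, it would have been W + L. There are three cases:
- W > U: classed late, inside the leakage question.
- W ≤ U and W + L > U, that is U − L < W ≤ U: not classed late, and outside the question *because* it leaked.
- W + L ≤ U: not classed late, and outside the question whatever became of the leaked fluid.

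The second case is a weight band of width L just below the limit. It exists for every L > 0 and every dressing size.

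**Step 2. Illustration (assumed values).** Take a 10x10 cm dressing, U = 26 g, weighed at W = 25 g after leaking L = 5 g. It lies within 11-26 g and is classed correct. With the 5 g retained it would weigh 25 + 5 = 30 g, which is above 26 g and so late. For L = 5 g the affected band is 26 − 5 = 21 g up to 26 g; for the other sizes it is 62 − 5 = 57 g up to 62 g and 109 − 5 = 104 g up to 109 g (lower ends excluded).

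**Step 3. Maceration.** Maceration does not itself change W. It falls outside the question whenever the dressing weighs U or less, including when it accompanies a leak in the second or third case.

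**Step 4. Consequence of lateness.** The objective yields the number of events among late changes. To say anything about lateness, that number has to be set beside the number among changes that were not late. Section 1.1 does not ask for the second number, although 1.2 records weight, wound status and incidents at every change.

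**Step 5. Frequency.** The document gives neither the proportion of changes expected to be late nor the proportion of other dressings that leak. It also does not say how the limits relate to absorbent capacity. The number of the 18 changes affected cannot be derived, and no probability is offered.

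**The case against.** The strongest reply is that late change is the stated subject of the objective, with leakage and maceration listed as possible consequences. On that reading the restriction is the intended scope, and asking about leakage at all changes is a different, broader question. This stands in part: the objective is not internally contradictory. But if the subject is the consequences of lateness, the other changes are needed as context, and a class that leakage itself can lower is a poor gate to the question.

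Second, 1.1 never points to Table 1, and the weight intervals are introduced to judge display activation. A visibly leaking dressing might have been treated as late whatever its weight. This also stands as a caution. Yet no other definition is given; if another was meant, 1.1 needs to state it.

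Third, a reader might infer that leaks at or below the limit go unrecorded. The protocol does not support that. Wound status and incidents are recorded at each change, and nothing forbids describing such a leak. The gap is in what the objective asks for, and probably not in data capture. Whether the forms carry an explicit leakage or maceration item cannot be told, because they are not shown.

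Fourth, tabulation by class is a detail that an analysis plan may supply. That is fair for the layout of a table, but the restriction to late changes is written into the protocol's objective itself.

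**Conclusion.** The point holds as a minor one. Read with the only definition available, 1.1 asks about leakage and maceration in a class that a leak can move a dressing out of, and it omits the changes that would put late ones in context. This rests on one inference, that the term in 1.1 means the Table 1 class, and on the stated content of the weight.

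Two stronger conclusions might be drawn and are not supported. One is that many leaks will be missed: the frequency is unknown, and any figure would only restate an assumed rate. The other is that the weight classification is faulty: the primary objective relates display activation to the saturation of the dressing, for which the retained liquid is the relevant quantity, so it is unaffected. No error rate, sample size or pass/fail criterion changes. The size is limited to one secondary descriptive objective over 18 planned changes.

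**What to change.** Reword 1.1 so that leakage and maceration, and their effect on the wound and surrounding skin, are described for all dressing changes and reported as counts in each Table 1 class (too early, correct, too late), without tests. State in 1.1 that lateness is defined by Table 1, if that is what is meant. Add a note that the weight of a leaking dressing understates the exudate load. Present the counts as description only; with 18 changes in 6 patients they give context for the late changes and do not prove a cause. Leave the Table 1 limits and the primary classification as they are.

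The cost is one sentence in 1.1, one descriptive table and, if the forms lack it, one explicit leakage and maceration item per change. No patients or visits are added. Much of the protocol is in the past tense; if data collection is over, no form item can be added, and the table should be built from existing records only, with the wider scope marked as decided afterwards.

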1.2 Design and endpoints

Patients with exuding leg ulcers were included from two different study sites for the clinical investigation. The clinical investigation is a small, explorative study which aimed to include 6 patients. To complete the study each patient underwent three dressing changes with the investigational device. Both study product versions, Variant A and Variant B, were used on each patient, either in order A-B-A or B-A-B. Amount and type of exudate might change over time, in this way the same variant is used at start and end to detect any changes in results. The aim was to get as many observations from Variant A and Variant B respectively.

Between dressing changes the patients were instructed to monitor the display and note if a blue drop (display activation) appeared. At each dressing change the patient and the caregiver checked the display for activation, weighed the dressing, recorded the wound status and eventual incidents.

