1.8 Amendments

For detailed descriptions of the amendments to the first version of the clinical investigation plan (CIP), see respective version. The main updates and reasons for updates are described here:

- **Version 2.0:** Updated according to requests for supplements by the Swedish Medical Products Agency to clarify some sections in the text.
- **Version 3.0:** Small updates before start of clinical investigation to clarify some sections in the text. Addition of signature page for the principal investigator.
- **Version 3.1:** Update of the acceptance limit for determination of correct change intervals. This was done before start of clinical investigation.
- **Version 4:** Inclusion of one more size, 20x20 cm, of the dressing DryMax Extra Soft used in the clinical investigation. The expected duration of the study changed from 6 months to 18 months, since the first 8 months included only 1 patient.
- **Version 5:** Inclusion of one more study centre; S2Clinic in Linköping to the clinical investigation.

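### Does leaving the split between A-B-A and B-A-B patients unstated defeat the aim of equally many observations per variant?

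*Protocol*

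**What the plan says.** Section 1.2 of the protocol sets the size: "The clinical investigation is a small, explorative study which aimed to include 6 patients". Each patient goes through three dressing changes to complete. On order it says: "Both study product versions, Variant A and Variant B, were used on each patient, either in order A-B-A or B-A-B". The reason given is that "Amount and type of exudate might change over time", so the variant used first is used again last in order to reveal a change. The section then states the aim: "The aim was to get as many observations from Variant A and Variant B respectively". It also says: "Patients with exuding leg ulcers were included from two different study sites for the clinical investigation".

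Section 1.8 shows that the second site came late. Version 4 lengthened the study from 6 to 18 months, "since the first 8 months included only 1 patient", and Version 5 brought "Inclusion of one more study centre".

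Section 1.3 says of the analysis that "no statistics are relevant to calculate". It disclaims any aim of a significant difference between the variants and describes the data as input to a broader assessment.

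No section says how many patients were to have each order, who or what decided the order, or how this was coordinated between sites.

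**The concern.** Three changes cannot be shared equally between two variants, so every patient gives one variant two observations and the other only one. Equality can arise only across patients, and only if the two orders are used equally often. With slow recruitment and a second site joining late, that does not happen by itself. For example, if each site alternated separately and both began with A-B-A, enrolment of 3+3 or 5+1 would put four patients on A-B-A and two on B-A-B.

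Two things could then be at stake. If the person treating the wound chose the order, the wound could influence which variant was used twice. And if the chance of correct activation differed between the middle change and the outer two, an unequal split would mix that difference into a comparison of the variants. The primary objective asks which variant activates correctly, and six completing patients give only 18 observations.

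**Working it through.** **Inputs.** Six planned patients, three changes each, orders A-B-A or B-A-B (all section 1.2). The protocol states no count per variant, so there is no figure to reproduce.

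**Counts.** Let k of six completing patients have A-B-A and 6 − k have B-A-B.

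- A observations: 2k + (6 − k) = 6 + k
- B observations: k + 2(6 − k) = 12 − k
- Equality: 6 + k = 12 − k, so k = 3

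| A-B-A : B-A-B | A : B observations |
|---|---|
| 3:3 | 9:9 |
| 4:2 | 10:8 |
| 5:1 | 11:7 |
| 6:0 | 12:6 |

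The reverse splits mirror these. With an odd number of completers exact equality is impossible.

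**How likely is a miss?** The document does not support a probability. Purely for scale, if each order were an independent even-chance draw (an assumption), 3:3 would occur with probability 20/64 = 0.3125, and 5:1 or worse in either direction with probability 14/64 = 0.219.

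**When would an unequal split distort the comparison?** Suppose the variants do not differ, let p1, p2 and p3 be the rates of correct activation at the three changes, and let d = (p1 + p3)/2 − p2. Pooling all observations per variant gives:

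- Mean for A: [k(p1 + p3) + (6 − k)p2]/(6 + k) = p2 + 2kd/(6 + k)
- Mean for B: [kp2 + (6 − k)(p1 + p3)]/(12 − k) = p2 + 2(6 − k)d/(12 − k)
- Difference: d[2k/(6 + k) − 2(6 − k)/(12 − k)]

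This is:

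- 3:3: d(6/9 − 6/9) = 0
- 4:2: d(8/10 − 4/8) = 0.30d
- 5:1: d(10/11 − 2/7) = 0.62d
- 6:0: d(12/12 − 0) = 1.00d

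For a steady, linear change over the three dressings d = 0, and the difference is zero at every split. The document gives no value for d.

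**What if results are read by order?** With a true variant difference v, and effects that simply add, the A-minus-B contrast within a patient is v + d on A-B-A and v − d on B-A-B. The average of the two order-specific contrasts is [(v + d) + (v − d)]/2 = v. So d drops out at any split that uses both orders, not only at 3:3.

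**The case for a change.** The best case for a change is that the order of treatment and its assignment belong to the design and are not normally left to an analysis plan. Section 1.2 sets an aim without the condition needed to reach it. Because section 1.3 foresees no statistical adjustment, balance would have to come from the design. A six-line shared list would be cheap. And although each patient receives both variants, the document does not commit to a within-patient reading.

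Of this, the counting stands, and so does the observation that the text shown gives no split and no assignment rule. The rest does not carry far:

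- Section 1.2 contains nothing false and no contradiction. Two mirrored orders in an even number of patients, with an aim of equality, lead a sensible reader to three and three.
- The text is in the past tense. Section 1.8 refers to the versions of the clinical investigation plan for detail on the amendments. Those are not shown and may hold the rule. A list drawn up in advance cannot be added to a study described as already carried out.
- No section says that staff chose the order, that sites alternated separately, or that results were pooled per variant. Without those suppositions only the table of possible counts remains.
- A 3:3 list would not cure pooling: at 9:9, six of the nine A observations but only three of the nine B observations come from A-B-A patients. Reading results within patient and by order deals with that, and it is a presentation matter commonly left to the analysis plan.

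The phrase about as many observations is also loose enough to mean as many as possible from each variant, in which case equality was never promised. I take equally many as the more natural reading, because the sentence ends with the word respectively.

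**Conclusion.** No change to the plan is called for. This is missing detail in a brief account, of a kind that those running and analysing the study can fill sensibly.

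In size, the gap is the difference between 9:9 and, at the extreme, 12:6 among 18 observations, so the less-used variant still has at least six. A bias in the variant comparison needs all of the following together: an unequal split, a non-linear change over the three dressings, and a summary that does not separate the orders. Wound-driven choice of order would be a further route. The document states none of these. Moreover, section 1.3 judges saturation from the weight of the used dressing, so a change in exudate does not by itself alter whether the display agreed with the dressing's state.

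This rests on six patients completing all three changes, on reading the aim as equal numbers, and on the study remaining descriptive, as section 1.3 says. A confirmatory comparison of the variants would need a stated allocation rule. Here, giving the split achieved, how order was decided, and results by patient and order would help readers, but it would not clearly alter any conclusion.

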1.3 The clinical investigation hypothesis or pass/fail criteria

The activation of the display in relation to the level of saturation of the wound dressing is determined by weighing the dressing after use which is then checked against the specified intervals in the Table below. The level of saturation is deemed to be in correct interval if the weight of the study product (Absorbest Fuktsensor + DryMax Extra Soft) is in the interval 11-26 g for 10x10 cm, 17-62 g for 10x20 cm and 26-109 g for 20x20 cm.

Table 1. Intervals to determine saturation level of the used dressing. Weight includes dressing dry weight and absorbed liquid

Dressing size	Changed too early	Interval for correct change	Changed too late
	Weight of dressing [g]		
10x10 cm	<11	11-26	>26
10x20 cm	<17	17-62	>62
20x20 cm	<26	26-109	>109

Since the study is small, explorative and observational, no statistics are relevant to calculate. The study does not aim to achieve statistical significance between Variant A and Variant B, but to collect data which should form the basis for a comprehensive assessment of the function of the different variants.

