1.5 Inclusion and exclusion criteria's

All patients had to fulfil the inclusion criteria, not have any of the exclusion criteria and give written informed consent. All patients were informed that the participation was voluntary, and they had the right to withdraw whenever wanted.

Inclusion criteria:

- Male or female, ≥18 years.
- Presence of moderate to high exuding leg ulcer, according to the clinician's assessment.
- The wound is deemed suitable for treatment with study product.
- The participant has given a written informed consent to participate in the study.

Exclusion criteria:

- Known pregnancy at the inclusion visit.
- Prisoner.
- Bleeding from the wound surface.
- The leg ulcer that is relevant for inclusion in the study is larger than 16x13 cm.
- Known or suspected hypersensitivity to the study products or its components.
 Components of DryMax Extra Soft: Polypropylene nonwoven outer cover, sodium polyacrylate and viscose-polyester as core material. Hot-melt glue seals the outer cover.
 Components in Absorbest Fuktsensor: PET-plastic in sensor and presence of small amounts of carbon, zinc, manganese dioxide, silver, conductive colour inks and electrolyte solution.
- Mental inability, reluctance or language difficulties that cause difficulties in understanding the meaning of participating in the study.
- The wound is infected.
- Illness or treatment of an indication other than the wound and which, according to the study personnel, can affect the wound treatment, the study and/or the dressing.

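### Do the saturation intervals in Table 1 need correcting because their widths do not scale consistently across the three dressing sizes?

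*Protocol*

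**What the plan says.** Protocol section 1.3 sets the saturation standard for the primary objective. The sensor and dressing are weighed together after use, and the level counts as correct when the weight "is in the interval 11-26 g for 10x10 cm, 17-62 g for 10x20 cm and 26-109 g for 20x20 cm". Table 1 repeats these limits, with lighter dressings graded as changed too early and heavier ones as too late. Its caption adds: "Weight includes dressing dry weight and absorbed liquid".

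Three other places bear on the point:
- Section 1.5, in the exclusion criterion on hypersensitivity, lists the dressing's components, including "sodium polyacrylate and viscose-polyester as core material".
- Section 1.8 records an update of the limits in Version 3.1, before the investigation started. For Version 4 it records "Inclusion of one more size, 20x20 cm, of the dressing DryMax Extra Soft used in the clinical investigation". It refers the reader to each version for detail.
- Section 1.1 has the secondary objective "To study the consequences in case the dressing has been changed too late", with leakage and maceration examined in those cases.

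The protocol gives no dry weight, sensor weight, core dimensions or absorbent capacity for any size, and no rule linking the three rows.

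**The concern.** Table 1 alone turns a weight into a grade. Dry weight and sensor weight are fixed within a size, so they cancel when the lower limit is subtracted from the upper. The width of each interval is therefore the range of absorbed liquid accepted as correct. For three sizes of one product with one listed core material, a reader expects these widths to follow the absorbing area. They do not, and the middle size looks too wide beside the largest.

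If the 10x20 cm row held a slip, dressings of that size would be judged more leniently than the others. An upper limit set too high would also keep some dressings out of the group examined for leakage and maceration. Six patients with three changes each give 6 x 3 = 18 dressings, so a few regraded dressings would be visible.

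**Working it through.** **Inputs.** The six limits are from section 1.3, where text and Table 1 agree on all of them. Nominal areas are 100, 200 and 400 cm2.

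**Widths (upper minus lower limit).**

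| Size | Width (g) | Width per nominal cm2 (g) |
|---|---|---|
| 10x10 cm | 26 - 11 = 15 | 15/100 = 0.150 |
| 10x20 cm | 62 - 17 = 45 | 45/200 = 0.225 |
| 20x20 cm | 109 - 26 = 83 | 83/400 = 0.2075 |

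The steps are 45/15 = 3.00 and 83/45 = 1.84. The protocol states no width or scaling rule, so there is no stated figure to reproduce beyond the limits themselves.

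**Test that needs least geometry.** Assume the same border in every size and the same liquid per cm2 of core. Let m be the total non-absorbing margin along one side. From 10x20 to 20x20 cm the core grows by (20 - m)/(10 - m) = 2 + m/(10 - m), which is at least 2 for any m of zero or more. The 10x20 cm width can then be at most 83/2 = 41.5 g. The stated 45 g is 3.5 g above that, and 45/41.5 = 1.08. If each limit is rounded by up to 0.5 g, each width can shift by 1 g. The ratio then reaches at most 84/44 = 1.91, still below 2, and the smallest excess is 44 - 84/2 = 2 g.

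**Size of the misfit under fuller models.**
- *Same border on all sides.* The cores are (10 - m)^2, (10 - m)(20 - m) and (20 - m)^2, so the middle width is the geometric mean of the other two: sqrt(15 x 83) = 35.3 g. Then 45/35.3 = 1.275, about 28% more. With rounding the range is 44/sqrt(16 x 84) = 1.20 to 46/sqrt(14 x 82) = 1.36. The fitted m is 2.61 cm.
- *Straight line in area.* 15 + 100 x (83 - 15)/300 = 37.7 g, and 45/37.7 = 1.19.
- *Different borders in the two directions.* The extreme case has no border in one direction and gives 2 x 15 = 30 g or 83/2 = 41.5 g. The excess runs from 45/41.5 = 1.08 to 45/30 = 1.50.

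The misfit is thus 8% to 50%, depending on a geometry that the protocol does not describe.

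**Which row is odd?** The geometric-mean relation can be solved for each row in turn.
- Taking 10x10 and 10x20 cm as right gives m = 5 cm and a 20x20 cm width of 45^2/15 = 135 g. The stated 83 g would be 39% too narrow (83/135 = 0.615).
- Taking 10x20 and 20x20 cm as right gives a 10x10 cm width of 45^2/83 = 24.4 g. The stated 15 g would again be 39% too narrow (15/24.4 = 0.615). This needs m = -1.84 cm, so a common border cannot explain it, though size-specific cores could.

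Two parameters fitted to two rows always leave the third as the misfit. The 10x10 and 20x20 cm rows themselves differ per nominal cm2 (0.2075/0.150 = 1.38) and agree only once a border is assumed.

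**The case for a change.** The best argument for acting is that the central inequality does not depend on the 28% figure. No shared non-negative border with equal loading, whether or not it is the same in both directions, gives 45 g beside 83 g, and rounding does not rescue it. The protocol itself fixes these limits, so they are not a matter left to a SAP. Section 1.8 shows that they were revised once and that a size was added later, which is how rows can drift apart. The lower limits nearly fit a geometric mean (sqrt(11 x 26) = 16.9 against 17 g), while the upper ones do not (sqrt(26 x 109) = 53.2 against 62 g), which hints at the 10x20 cm upper limit. Checking would be cheap if the capacity data exist.

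The inequality stands. It shows that the rows do not come from one border and one loading, but not that any row is wrong. Cores or borders that differ by size, or limits set by bench test or by the sensor's trigger point, would give such widths without error. Section 1.5 names materials only; it says nothing of core weight or layout by size. The hint about the upper limit is weak, because whole weights include dry and sensor weight and need not follow a geometric mean.

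**Conclusion.** No change to the plan follows. The widths scale unevenly, by at least 3.5 g in the 10x20 cm row relative to the 20x20 cm row (2 g after rounding), if border and absorbency per cm2 are common to all sizes. The protocol asserts neither, so this is a mismatch with an outside model and not a contradiction within the document. Misgrading is not shown, and neither the row nor the limit at fault, if any, can be identified.

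What remains is an unstated derivation. It may be recorded in the plan versions to which section 1.8 refers, which are not at hand. Writing it down would change no grade if the limits rest on size-specific capacity; if no such data exist, it would need bench measurements.

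The practical exposure is limited. Section 1.2 has every dressing weighed, and a grade cannot be assigned without knowing the size, so grades can be reassigned should a row prove wrong. Each patient uses both variants. If a patient keeps one size throughout, which is not stated, both variants face the same interval. A wide interval could blunt a difference between them but would not apply a different standard to either. Section 1.3 plans no statistical comparison that a few regraded dressings would overturn.
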